2. INTRODUCTION

2.1 Myocardial Infarction: The clinical risk remains high post the acute event

[figure not shown]
A recent update of US Medicare records was published that evaluated data involving 350,509 acute myocardial infarction (MI) hospitalization in patients ≥ 65 years who were discharged alive after their event.³ Within the first year post the index event, 25.9% of the MI patients died with 50.5% re-hospitalized. In the month after a MI, the likelihood of death was 21 times higher and the likelihood of hospitalization was 12 times higher than among the general Medicare-age population. Similar one year mortality data have been published for patients post STEMI treated in Canada.⁴ Clearly, despite important advances in standard of care therapies, there remains a large unmet clinical need to reduce death and re-hospitalization post MI. Stem cell therapy, especially with allogeneic cells, represents an innovative opportunity to explore early therapeutic approaches that would be adjunctive to coronary artery revascularization of the culprit lesion with the goal of reducing post MI adverse myocardial remodeling and major adverse cardiovascular events.⁵⁻¹⁰

In patients with acute ST-segment elevation myocardial infarctions (STEMI), there is a progression of myocardial injury that begins with the onset of cardiac ischemia and continues past the time of coronary reperfusion.¹¹ The adage that “Time is Tissue” remains a basic approach to patients with STEMI with the emphasis on timeliness of reperfusion therapy. The 2013 ACCF/AHA STEMI Management Guidelines state that “for patients with STEMI, an ideal first-medical contact to device time goal is 90 minutes or less”.¹² This equates to a goal of onset of ischemic symptoms to device time of ≤ 120 minutes. When this cannot be achieved, the Guidelines further emphasize that “Reperfusion therapy should be administered to all eligible patients with STEMI with symptom onset within the prior 12 hours”. Because the pathophysiologic processes that include necrosis and apoptosis evolve over time, it is important to consider the duration of myocardial ischemia as an important variable in subsequent analyses of the natural history of myocardial infarctions with and without specific interventions.¹³⁻¹⁶

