6.1.1.5 Visit 5: Two thru Seven Days Post Study Infusion

- Daily physical examination to include but not limited to examination of the cardiac, pulmonary, neurologic (including but not limited to mental status) and gastrointestinal systems. New physical examination findings of any system will be noted. In the event of abnormal neurological findings, subjects will require a neurological consultation.
- Recording of concomitant medications including vaccinations
- Daily vital signs (BP, temperature, heart rate and respiratory rate)
- 12 Lead ECG on Day 2 and prior to hospital discharge
- Daily telemetry monitoring
- Daily Troponin I (or T)
- Daily creatine kinase MB fraction
- Daily AE/SAE assessment
- Hospital Discharge on Day 4-7 with outpatient 48 hour Holter monitor
- **The target date for the following assessment is Day 3 post study infusion \pm 1 day:**

- Basic Metabolic Profile (sodium, potassium, chloride, carbon dioxide (CO₂), blood urea nitrogen (BUN), glucose, calculated GFR, creatinine and calcium)
- hs C-reactive Protein (CRP)
- Hepatic function profile (total protein, albumin, alkaline phosphatase, alanine transaminase, aspartate aminotransferase, direct bilirubin, total bilirubin)
- CBC with differential and platelets
- NT-Pro Brain Natriuretic Peptide, type B
- 2D echocardiogram
- Cardiac MRI
- Canadian cardiovascular society angina classification (CCS)
- NYHA Classification
- Weight.

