7.5 Blinding and Randomization

This is a double blinded study. Each subject will be blinded to his/her assigned treatment. Study blinding will be maintained as described below.

Blinded Study Personnel and Participants

Subjects, Site personnel, Investigators will remain blinded until after all safety follow-up is completed. The DSMB may choose to be unblinded.

Unblinded Study Personnel

Pre-specified unblinded clinical operations and biometrics team members at both the vendor and sponsor will have access to the unblinded efficacy results.

These pre-specified unblinded team members will be identified prior to the analysis being conducted and they will not have any operational responsibility for the conduct of the study.

An independent unblinded statistician from the CRO will support the DSMB by providing Open and Closed Reports to the DSMB independent statistician based on the best available data and other information to the DSMB.

Subjects that are admitted within a maximum of 12 hours after onset of ischemic cardiac symptoms who are experiencing a *de novo* anterior MI and qualify based on inclusion/exclusion criteria will be approached for enrollment. Eligible subjects will be randomized to receive one of three possible intracoronary treatments: Investigational product at 12.5 M or 25.0 M allogeneic MPCs or saline placebo control.

Randomization will occur after informed consent has been obtained and the PCI with stenting of the culprit LAD coronary artery lesion has been successfully completed (residual TIMI Flow Grade 3 or 2, residual diameter stenosis <20% by QCA, uncomplicated primary PCI).

The randomization and treatment assignment will be obtained from an IVRS/ IWRS.

The following stratification for duration of cardiac ischemia will be performed to ensure balanced randomization across the treatment groups:

- ≤ 2 hours
- >2 hours to ≤ 6 hours
- >6 to ≤ 12 hours.

After randomization has been performed, each subject will receive a unique identification number that will include site and subject identifiers.

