8.2 Secondary Efficacy Endpoints

- The change in LVESV as assessed by 2D-echocardiography from baseline to 6 months post investigational agent infusion.
- The change in relative infarct size as assessed by late contrast enhancement MRI (% infarct volume/total LV tissue volume) from baseline to 6 months post investigational agent infusion.
- Additional functional efficacy endpoints will be assessed with the following diagnostic studies:
 - Cardiac MRI at 2-4 days, 30 days and at Month 6.
 - LVEF
 - LVESV
 - LVEDV
 - Left ventricular wall thickness and thickening in all segments including infarct area
 - Regional wall motion score
 - Myocardial MVO measured as reduced signal intensity in the region of interest
 - MI size measured in the region of interest as late contrast enhancement
 - Myocardial salvage index
 - 2D echocardiogram at 2-4 days, 30 days and at Month 6.
 - LVEF
 - LVESV
 - LVEDV
 - Cardiac dimensions (LVESD/ LVEDD)
 - Regional wall motion score index
 - If neither MPC arm is found to be better than the placebo arm and there is no difference between the MPC groups (using the ANCOVA test with alpha=.1) in the effect on LVESV then the pooled MPC group will be compared to the placebo group for all functional parameters.
 - A subset analysis that corresponds to the stratification used during randomization will be performed. Stratification will be based on the following following categories defined as time from onset of AMI symptoms to PCI:
 - ≤ 2 hours
 - > 2 hours to ≤ 6 hours
 - > 6 to ≤ 12 hours.

- In addition, a subset analysis will be evaluated at the following ischemia duration time points:
 - ≤ 6 hours
 - > 6 to ≤ 12 hours.
- NT-Pro-BNP serum levels (as measurement biomarker for heart failure) at baseline, days 2-4 and 30 and months 3 6, 12 and 24
- Score changes for TIMI Myocardial Flow Grade and Perfusion assessments at the following day 0 time points:
 - pre-PCI,
 - immediately post-PCI,
 - after approximately 50% of intracoronary infusion of investigational agent,
 - at completion of intracoronary infusion of investigational agent.

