11.2 Statistical Methods

The primary efficacy analysis will use an ANCOVA model with baseline LVESV as covariate and alpha=0.05 to test for a difference of change in LVESV from baseline to Month 6 between each MPC arm separately and the placebo arm. If neither MPC arm is found to be better than the placebo arm and there is no difference between the MPC groups (using the ANCOVA test with alpha= 0.1) in the effect on LVESV, then the pooled MPC group will be compared to the placebo group for all functional parameters.

All other statistical tests will be considered to be exploratory (post-hoc) unless a pre-specified hypothesis exists in the statistical analysis plan (SAP), which will be finalized prior to any analysis. All statistical tests will be two-sided and statistical significance will be assessed with

respect to a nominal p-value ≤ 0.05 . Any deviations from the planned analyses will be documented and justified in the final clinical/statistical study report.

The primary efficacy analysis for LVESV will be performed using cMRI collected data. The secondary efficacy analyses for LVESV will be performed using ECHO data alone, as well as ECHO data as a substitute for missing cMRI data at baseline and/or at Month 6.

In the latter case, a regression equation will be determined between measurements for LVESV-cMRI and LVESV-ECHO over a range of values. Whenever appropriate and based on LVESV-ECHO values generated using the regression equation, a LVESV-ECHO “corrected” value will be determined and used as a replacement for missing value for LVESV-cMRI.

When all enrolled subjects have completed the study through Visit 9 (Month 6), an unblinded analysis of the safety and primary and secondary efficacy endpoints will be conducted.

The primary and secondary efficacy analyses will be performed using data collected through Visit 9 (Month 6). In addition, safety analyses will be performed on all available data through Visit 12 (Month 24) at the time of conduct of the efficacy analysis. In addition, the final safety analysis will be performed at 24 months for all patients.

No additional efficacy data will be collected beyond Visit 9 (Month 6) except for cardiac biomarkers.

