11.5 Determination of Sample Size

To detect a treatment effect of 10.0 ml for LVESV (SD 14 ml), [REDACTED] as well as published clinical data ^{1-3, 58,59}, with a two-sided 5% significance level and a power of 80%, a sample size of 105 subjects will be necessary, given the observed dropout rate of approximately 4%. Of these, approximately 70 will receive MPCs (35 to receive 12.5 M MPC and 35 to receive 25M MPC) and 35 will receive placebo and act as control subjects.

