11.8 Efficacy and Feasibility Analyses

Where appropriate, 95% confidence intervals for treatment differences in key feasibility measures will be constructed. Analysis of covariance (ANCOVA) may be used where appropriate to adjust for baseline differences in key continuous feasibility outcome measures and also take the site and the time from onset of AMI symptoms to PCI as covariates in the ANCOVA model. For non-normally distributed measures, the Wilcox-Mann-Whitney test or analysis of variance ANOVA of rank transformed data may be used as an alternative. For categorical measures, relative risks and nominal 95% confidence intervals will be constructed to assess strength of association. The Cochran-Mantel-Haeszel test (CMH) controlled by site and the time from the onset of AMI symptom to PCI will be used for the treatment differences. The primary feasibility analysis will be performed on the FA population, and confirmatory based on PP population.

The primary and secondary efficacy analyses will be performed on ITT, FA, and PP populations. Analysis of clinical endpoints will be performed on all analysis populations.

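### Randomization is stratified by ischemia duration, but the primary LVESV ANCOVA omits the stratum; if the stratum predicts change beyond baseline, the reported standard error is too large and some power is lost

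*Combined protocol and SAP*

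**What the plan says.** Section 7.5, like the synopsis and section 4.3, stratifies the 1:1:1 randomization into three bands (up to 2 hours, over 2 to 6, over 6 to 12): "The following stratification for duration of cardiac ischemia will be performed to ensure balanced randomization across the treatment groups". Section 2.1 gives the reason, saying that "it is important to consider the duration of myocardial ischemia as an important variable in subsequent analyses".

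The primary model in section 11.2 does not carry this through: "The primary efficacy analysis will use an ANCOVA model with baseline LVESV as covariate and alpha=0.05". It is applied to each MPC arm against placebo, and no stratum term is named.

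Ischemia duration is used in three other places:

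- Section 8.2, for subgroups: "A subset analysis that corresponds to the stratification used during randomization will be performed". The same section defines the bands by time from symptom onset to PCI, so this is the same quantity as the stratification factor.
- Section 11.8, in an optional ANCOVA for continuous feasibility outcomes, which may "also take the site and the time from onset of AMI symptoms to PCI as covariates in the ANCOVA model".
- Section 11.8, in a Cochran-Mantel-Haenszel test for categorical measures, "controlled by site and the time from the onset of AMI symptom to PCI".

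None of these puts the stratum in the primary LVESV model. Section 11.2 refers to a SAP to be finalized before any analysis, but the text available has no separate SAP section that adds it.

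**The concern.** When allocation is balanced within strata, differences between strata largely cancel out of the comparison between arms. The treatment estimate then varies less from trial to trial than it would under simple randomization. An ANCOVA without the stratum does not see this: the between-stratum variation stays in the residual mean square, and the standard error is computed as if that variation could still fall unevenly between arms.

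If ischemia duration predicts LVESV change beyond baseline LVESV, the reported interval is too wide and the test rejects less often than its nominal level. The same applies to the between-dose test at alpha 0.1, which is one of the conditions for pooling the MPC arms. If the doses are truly equal, they would pass that condition somewhat more often than the nominal level implies.

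At stake is efficiency and an accurate standard error. There is no bias and no inflation of the false-positive rate.

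**Working it through.** **Inputs from section 11.5.** Difference 10 ml, SD 14 ml, two-sided 5%, power 80%, about 4% dropout, 105 subjects in three arms of 35. Evaluable per arm: 35 × 0.96 = 33.6.

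**Assumed, not in the documents.** R² is the share of the LVESV-change variance left after baseline LVESV that the stratum explains; it is varied from 0 to 15%. The 14 ml is taken as the SD after baseline adjustment. The simulations also need block size and stratum shares.

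**Reproducing the plan's figure.** The plan states "with a two-sided 5% significance level and a power of 80%, a sample size of 105 subjects will be necessary".

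- Normal approximation: n = 2 × (1.960 + 0.842)² × 14² / 10² = 30.8, so 31 per arm. Then 31 / 0.96 = 32.3, so 33 per arm, 99 in total.
- Exact t-test: 32 per arm. Then 32 / 0.96 = 33.3, so 34 per arm, 102 in total.

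The plan's 105 is one subject per arm above the t-test answer, so the figure reproduces. With 33.6 evaluable per arm, power is 83.3% (normal) or 82.2% (t).

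**Effect of leaving the stratum out, assuming perfect balance within strata.**

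- Reported SE = 14 × √(2/33.6) = 3.42 ml, whatever R² is.
- True SE = 3.42 × √(1 − R²).
- Actual type I error = 2 × [1 − Φ(1.96 / √(1 − R²))].
- Power without stratum = Φ[(10 / reported SE − 1.96) / √(1 − R²)].
- Power with stratum = Φ(10 / true SE − 1.96).

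Worked line at R² = 0.10, where √0.90 = 0.949 and 10/3.416 = 2.927:

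- without stratum: (2.927 − 1.960) / 0.949 = 1.020, so 84.6%;
- with stratum: 2.927 / 0.949 − 1.960 = 1.126, so 87.0%.

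| R² | True SE (ml) | Reported SE too large by | 95% half-width without / with (1.96 × SE, ml) | Type I without stratum | Power without / with | Gain (points) |
|---|---|---|---|---|---|---|
| 0 | 3.42 | 0% | 6.7 / 6.7 | 5.0% | 83.3 / 83.3% | 0 |
| 0.05 | 3.33 | 2.6% | 6.7 / 6.5 | 4.4% | 84.0 / 85.2% | 1.2 |
| 0.10 | 3.24 | 5.4% | 6.7 / 6.4 | 3.9% | 84.6 / 87.0% | 2.4 |
| 0.15 | 3.15 | 8.5% | 6.7 / 6.2 | 3.4% | 85.3 / 88.8% | 3.5 |

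**Simulation check.** 12,000 trials per setting: three arms, 105 randomized, 4% dropout, permuted blocks of 6, strata 25/50/25%. Results at R² = 0, 0.05, 0.10, 0.15:

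- mean reported SE without the stratum: 3.42, 3.43, 3.43, 3.43 ml;
- empirical SD of that estimate: 3.43, 3.35, 3.28, 3.20 ml;
- type I error without the stratum: 5.0, 4.7, 4.2, 3.6% (5.1% throughout with it);
- power without the stratum: 81.8, 82.4, 83.0, 83.4%;
- power with the stratum: 81.6, 83.8, 85.8, 87.5%;
- gain, taken before rounding: −0.2, +1.3, +2.8, +4.1 points.

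Incomplete blocks and dropout make the balance slightly imperfect. The SE overstatement is therefore a little smaller than in the table: 3.43/3.35, 3.43/3.28 and 3.43/3.20 give 2.4, 4.6 and 7.2%. Other block sizes, stratum shares and independent runs gave gains of 1.1 to 1.4, 2.3 to 2.8 and 3.7 to 4.3 points at R² = 0.05, 0.10 and 0.15.

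**Between-dose test at nominal 0.1.** Replacing 1.96 by 1.645 in the type I formula gives actual sizes of about 10, 9.1, 8.3 and 7.4%.

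**The case against.** **Nothing is invalid.** The error is conservative, power stays above 80% without the stratum, and this is a Phase 2 trial whose primary objective is safety and feasibility. This stands: the point concerns efficiency.

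**The size rests on an R² that the documents do not give, and it could be zero.** Baseline imaging is done after infusion; section 6.1.1.5 says "The target date for the following assessment is Day 3 post study infusion", within a day either side. Baseline LVESV may by then already carry much of the ischemia effect. This stands too, which is why the range starts at zero. The direction does not depend on R², and at R² = 0 the change costs almost nothing.

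**The 14 ml may be the SD of change before baseline adjustment.** The synopsis wording leans that way. If baseline LVESV then explained an assumed 10, 20 or 30% of that variance, the same formulas at R² = 0.10 give power without the stratum of 88, 92 or 95% and gains of 2.0, 1.5 or 1.0 points. The percentage overstatement of the standard error does not change.

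**Section 11.8 may already cover it.** Its heading includes efficacy, and the feasibility endpoint defined in section 10.1 is TIMI flow, a grade, so the sentence on continuous outcomes might have been meant to reach LVESV. But it is optional, is written for feasibility outcomes and does not amend section 11.2. At most it leaves the primary covariate set open to two readings, which is a further reason to settle it.

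**The SAP may add the stratum.** It may. Part of the synopsis's statistical text is also missing from the copy available. The finding is therefore limited to the text that can be read, in which section 11.2 names baseline LVESV alone.

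**Conclusion.** The concern holds. The trial randomizes within three ischemia-duration strata, and the primary LVESV model does not include them. If the stratum explains 5 to 15% of the variance left after baseline LVESV, the reported standard error is too large by about 2.4 to 8.5% (simulation and closed form together). The nominal 5% test then runs at about 3.4 to 4.7%, and roughly 1 to 4 points of power are given up against the stratified analysis. If the stratum explains nothing, nothing is lost.

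These sizes depend on the assumed R² and on reading 14 ml as the SD after baseline adjustment; the other reading makes the power gain smaller. The sample size and the validity of the test are not in question. The change is worth making because it is nearly free and brings the primary model into line with the design.

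**What to change.** Before the unblinded Month 6 analysis, amend section 11.2 and the SAP so that the primary ANCOVA has treatment, baseline LVESV and the three-level ischemia-duration stratum as a fixed factor, using the stratum recorded at randomization. For consistency, use the same model for the between-dose test at alpha 0.1, the pooled comparison and the continuous secondary cMRI and echo endpoints.

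State in section 11.8 whether its covariate sentence applies to LVESV. A separate suggestion, which can be decided on its own, is to leave site out of the primary model: with about 25 sites and 105 subjects there are about 4 subjects per site (105/25 = 4.2), and site terms would use up to 24 degrees of freedom.

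The cost is one line of text and 2 degrees of freedom, about 0.1 to 0.2 points of power if the stratum explains nothing. No extra subjects or data are needed, because the randomization system already holds the stratum.

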Clinical Endpoints	
Clinical Endpoints will be assessed throughout the index hospitalization as well as at outpatient visits at 14 and 30 days, and at 3, 6, 12, 18 and 24 months after the index cardiac catheterization procedure, including:
 
 • Occurrence of MACCE including: 
 ◦ Cardiovascular death ◦ Non-fatal myocardial infarction ◦ Non-fatal stroke ◦ Cardiac hospitalization due to heart failure • Target vessel (or other vessel) revascularization post index cardiac catheterization and new or worsening heart failure during the index hospitalization will be tracked as “Adverse Events of Special Interest”. • Total number of subjects with documented ventricular arrhythmia (sustained and non-sustained VT/VF) throughout the study period. • Angina pectoris as defined by Canadian Cardiovascular Society (CCS) clinical clarification. • Functional status will be classified by the NYHA criteria.
Planned Analysis of Efficacy and Safety	
The primary efficacy analysis for LVESV will be performed using cMRI collected data. The secondary efficacy analyses for LVESV will be performed using ECHO data alone, as well as ECHO data as a substitute for missing cMRI data at baseline and/or at Month 6.
 
In the latter case, a regression equation will be determined between measurements for LVESV-cMRI and LVESV-ECHO over a range of values. Whenever appropriate and based on LVESV-ECHO values generated using the regression equation, a LVESV-ECHO “corrected” value will be determined and used as

	
a replacement for missing value for LVESV-cMRI.
 
When all enrolled subjects have completed the study through Visit 9 (Month 6), an unblinded analysis of the safety and primary and secondary efficacy endpoints will be conducted.
 
The primary and secondary efficacy analyses will be performed using data collected through Visit 9 (Month 6). Safety analyses will be performed on all available data through Visit 12 (Month 24) at the time of conduct of the efficacy analysis. In addition, the final safety analysis will be performed at 24 months for all patients.
 
No additional efficacy data will be collected beyond Visit 9 (Month 6) except for cardiac biomarkers.

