4.3 Study Design

This is a prospective, double blind, randomized, placebo-controlled, dose finding study that will enroll approximately 105 subjects with *de novo* anterior STEMI due to a lesion involving LAD coronary artery who undergo primary PCI at approximately 25 clinical study sites.

This study will compare two doses of MPCs and a placebo control group. Study subjects will be randomly assigned in 1:1:1 fashion to receive either 12.5 M or 25 M MPCs or placebo (saline). Each group will have approximately 35 subjects.

Potential subjects will be approached by the site investigator prior to PCI and must sign an informed consent form before initiation of the cardiac catheterization procedure in order to participate in this trial. Following successful and uneventful PCI and stenting of the culprit LAD lesion, the subjects will be randomized. The randomization and treatment assignment will be obtained from an IVRS/ IWRS. The following stratification for duration of cardiac ischemia will be performed to ensure balanced randomization across the treatment groups:

- ≤ 2 hours
- > 2 hours to ≤ 6 hours
- > 6 to ≤ 12 hours.

Eligible subjects will receive intracoronary delivery of the assigned treatment infused via a microcatheter into the stented culprit artery. The subjects randomized to MPCs will be infused at an infusion rate of 2 ml/min over approximately 60 minutes, including line flush [2.5×10^5 MPCs/min (12.5 M), 5.0×10^5 MPCs/min (25 M)]. The subjects randomized to placebo will be infused placebo solution at 2 mL/min over approximately 60 minutes, including line flush (0 MPCs/min). Due to the presence of a catheter in the coronary arteries for this period of time, anticoagulants should be given as clinically indicated. The MPC product (12.5M and 25M MPCs) and the placebo solution will be diluted in 100mL 0.9% saline solution prior to infusion. The Sponsor will provide all sites with blinded treatment cryobags or cryovials, which contain the different doses of MPCs or placebo solution.

An IC bolus of GTN/ NTG (100-200mcg) should be administered (blood pressure permitting) prior to TIMI flow assessments during the investigational agent infusion period as well as after completion of the investigational agent infusion and immediately prior to the final coronary angiographic imaging.

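### In the secondary LVESV analysis, a missing Month 6 cMRI value is filled by one echo-regression value treated as observed; on the natural reading this pulls the effect modestly toward zero, and multiple imputation would avoid it

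*Combined protocol and SAP*

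**What the plan says.** Section 11.2 and the synopsis (section 1.5, planned analysis of efficacy and safety) set out three LVESV analyses. The primary one uses collected cMRI values only, in an "ANCOVA model with baseline LVESV as covariate and alpha=0.05", comparing each MPC arm with placebo. Two secondary ones use echo alone, and echo as a stand-in where cMRI is missing at baseline, at Month 6 or at both.

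For the stand-in, "a regression equation will be determined between measurements for LVESV-cMRI and LVESV-ECHO over a range of values", and a corrected echo value is then "determined and used as a replacement for missing value for LVESV-cMRI", where judged appropriate. The text does not state which variable is regressed on which, whether arm, visit or other cMRI values enter, whether a residual is drawn, or how the uncertainty of the filled-in value is carried forward. Section 11.2 refers to a SAP to be finalized before any analysis; the documents contain no further detail on this step.

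The schedule (Table 2 and section 6.1) collects both cMRI and echo at about Day 3, at Day 30 and at Month 6. The footnote on the early termination visit says that neither scan is required there.

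**The concern.** A predicted value is less spread out than a measured one. When a line fitted to all arms together predicts cMRI from a noisy echo, each prediction is pulled toward the overall mean, so the predicted arms lie closer together than the true arms. The subject's own earlier cMRI, which carries much information about Month 6, is not stated to be used. The fitted value is then counted as a full observation.

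At stake is the reading of this secondary result. A somewhat smaller effect, or a non-significant one, could be taken as a real difference from the cMRI-only result when part of it comes from the fill-in method.

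**Working it through.** **Inputs from the documents.** "To detect a treatment effect of 10.0 ml for LVESV (SD 14 ml" (section 11.5), taken here as the SD of the change; "with a two-sided 5% significance level and a power of 80%, a sample size of 105 subjects will be necessary" (section 11.5); "All statistical tests will be two-sided" (section 11.2); allocation "randomly assigned in 1:1:1 fashion" (section 4.3), about 35 per arm; dropout about 4%.

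**The plan's own figure.** The normal formula gives n = 2 × (1.96 + 0.842)² × 14² / 10² = 30.8, so 31 per arm. Dividing by 0.96 gives 33 per arm, or 99 in all. The t-based version gives 32, then 34 per arm, or 102 in all, within 3% of 105. With 35 × 0.96 = 33.6 evaluable per arm, t-based power is 0.82. The design figure is reproduced, and nothing below changes it.

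**Assumptions not in the documents.** Cross-sectional LVESV SD S = 20 or 30 ml; cMRI–echo correlation ρ = 0.7 to 0.9; fraction filled in m = 10 to 30%; missing completely at random unless stated.

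**Shrinkage, Month 6 missing, cMRI regressed on echo.** Write echo = a + b × cMRI + noise.

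1. An effect of 10 ml on cMRI is 10b ml on echo.
2. The pooled slope of cMRI on echo is ρ²/b, so the filled-in values differ between arms by 10ρ² ml.
3. A fraction 1 − m carries 10 ml and a fraction m carries 10ρ² ml, so the expected effect is 10 × [1 − m(1 − ρ²)] ml.

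For example, m = 0.2 and ρ = 0.7 give 10 × (1 − 0.2 × 0.51) = 8.98 ml.

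| m | ρ = 0.7 | ρ = 0.8 | ρ = 0.9 |
|---|---|---|---|
| 10% | 9.5 ml | 9.6 ml | 9.8 ml |
| 20% | 9.0 ml | 9.3 ml | 9.6 ml |
| 30% | 8.5 ml | 8.9 ml | 9.4 ml |

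Simulation of the ANCOVA agrees with the formula.

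**Power at m = 20%.** Simulated, 35 per arm, 10 ml effect, 1,500 trials per setting. The multiple imputation used arm, baseline cMRI and Month 6 echo, with 20 draws.

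| S | ρ | Complete cases | Single substitution | Multiple imputation |
|---|---|---|---|---|
| 20 | 0.7 | 0.79 | 0.79 | 0.82 |
| 20 | 0.8 | 0.79 | 0.82 | 0.83 |
| 20 | 0.9 | 0.79 | 0.85 | 0.84 |
| 30 | 0.7 | 0.76 | 0.68 | 0.77 |
| 30 | 0.8 | 0.76 | 0.73 | 0.78 |
| 30 | 0.9 | 0.76 | 0.78 | 0.80 |

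Multiple imputation returned about 10.0 ml in every row. Repeats with 34 per arm at S = 30 and ρ = 0.7 gave about 0.65 for substitution against 0.73 for complete cases.

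The spread matters because the echo line predicts cMRI with error S√(1 − ρ²). At ρ = 0.7 this is 30 × 0.714 = 21.4 ml or 20 × 0.714 = 14.3 ml. The subject's own baseline predicts better. With a change SD of 14 ml, the correlation between visits is 1 − 14²/(2S²) = 0.891 at S = 30, which leaves 30 × √(1 − 0.891²) = 13.6 ml.

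**The other direction.** If echo is regressed on cMRI and the line is inverted, the slope is 1/b and the effect stays at about 9.8 to 10.1 ml. The error of the filled-in value rises to S√(1/ρ² − 1), which is 30 × 1.02 = 30.6 ml at S = 30 and ρ = 0.7. Simulated power at S = 30 was 0.54 to 0.58 at ρ = 0.7 and 0.66 to 0.68 at ρ = 0.8, below both alternatives.

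**Baseline only missing.** No shrinkage: 10.1 to 10.2 ml against 10.1 ml for complete cases. Power is not lower (0.78 against 0.77 at S = 30, ρ = 0.8, m = 20%).

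**Type I error at S = 30, ρ = 0.8.** Pooled substitution: 0.048 at m = 10% and at 30%. Multiple imputation at m = 20%: 0.059, against 0.060 for complete cases on the same data (simulation error about 0.006). A single deterministic value from a line that includes arm and baseline: 0.068, 0.091 and 0.139 at m = 10, 20 and 30%.

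**The case against.** A reader might infer that the primary result or the sample size is compromised. Neither is: the primary analysis uses collected cMRI only, no success rule depends on the echo substitution, and the documents do not say that it is there to rescue the primary endpoint.

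A reader might also infer that the method always shrinks the effect. The text does not fix the direction of the regression or its covariates, so the shrinkage belongs to the natural reading and not to every reading. This stands. The inverted line, however, exchanges shrinkage for noise and is no better, and substitution at baseline only does neither harm.

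A third tempting reading is that dropping subjects would be better. That holds only for wide LVESV spread with modest echo agreement, and only if scans are missing at random. When Month 6 scans were assumed missing more often in subjects with worse remodelling (about 22% missing), complete cases gave 8.0 to 8.2 ml and substitution 8.5 to 9.3 ml. Substitution had higher power in 8 of 9 settings. Multiple imputation was not among the methods compared there.

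Finally, the size is modest. Even a 1 ml loss compares with a standard error of about 14 × √(2/34) = 3.4 ml. The group with an echo but no usable cMRI may be small: expected dropout is about 4%, contraindications to cMRI are excluded, and subjects who leave early need have neither scan. All of this stands and limits the priority of the point. It does not remove the case for a method that is better specified and costs little.

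**Conclusion.** The point holds for the secondary analysis only. On the natural reading, with Month 6 values filled in, a 10 ml effect is expected to appear as 9.0 to 9.6 ml at m = 20%, and as 9.5 to 9.8 ml at m = 10%, for ρ between 0.7 and 0.9. The bias is toward no effect and creates no false-positive risk. Power is lost against complete cases at S = 30 and ρ of 0.8 or less, is about equal at S = 20 and ρ = 0.7, and is gained at ρ near 0.9. S, ρ, m and the missingness mechanism are assumptions. The formula also requires cMRI to be regressed on echo without an arm term.

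In the settings simulated, multiple imputation removed the shrinkage, kept type I error in line with complete cases, and had power equal to or above substitution within simulation error. The tested model was simpler than the one proposed below: it did not include Day 30 cMRI, ischemia stratum or echo at the other visits.

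**What to change.** In the SAP, replace the single substitution in this secondary analysis with multiple imputation of LVESV-cMRI. The imputation model should contain treatment arm, ischemia-time stratum, all observed cMRI LVESV values (about Day 3, Day 30, Month 6) and echo LVESV at each visit. Fit the planned ANCOVA in each completed data set and combine by Rubin's rules. State the number of imputations, and report how many values were imputed by arm and visit.

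Do not simply add arm to a single deterministic prediction: that removes the shrinkage but inflates type I error. Leave the cMRI-only primary analysis and the echo-alone analysis as they are.

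The cost is SAP wording and modest programming. No new data are needed, and section 11.2 already calls for a SAP finalized before any analysis.
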